1 INTRODUCTION

1.1 STUDY DESIGN

This is a Phase 4, 16 week, prospective, multicenter, interventional, open-label, single-arm study in insulin-naïve participants with very uncontrolled type 2 diabetes mellitus (T2DM) using blinded continuous glucose monitoring (CGM). The primary endpoint will assess the change of time in range (70-180mg/dL) between baseline and week 16 as measured by CGM in participants initiated on Soliqua 100/33. Background GLP-1RA (oral or injectable) and DPP-4i therapies will be discontinued prior to Soliqua 100/33 administration and sulfonylureas will be down-titrated by 50% when starting Soliqua 100/33. Continuous glucose monitoring measures will allow clinicians to frequently observe changes in glycemic control and variability including measures such as time in range (TIR), time below range (TBR) and time above range (TAR) with more granularity than the measure of HbA1c% alone. The Freestyle Libre Pro is a flash glucose monitoring device that collects glucose values every 15 minutes for up to 14 days. These values are charted into a single daily view, irrespective of the numbers of glucose values measured to provide a view of glycemic control and variability and assist clinicians for management of patients with diabetes.

[figure not shown]
All eligible participants will undergo 14 days of blinded continuous CGM monitoring and a mixed-meal tolerance test (MMTT) during the run-in period while on background medications. Soliqua 100/33 will be initiated, and dose will be adjusted during the 12-week titration period, at the investigator's discretion, until the desired fasting self-measured plasma glucose (SMPG) value (80-100 mg/dL) is achieved.

In order to attain a target fasting SMPG value of 80 to 100 mg/dL dose of Soliqua 100/33 will be adjusted based upon the median SMPG value. If the lowest value from the previous 3 measurements is from 80 to 100 mg/dL and the other 2 values are well above 100 mg/dL, further titration may be implemented at the investigator's discretion. If the lowest value is <70 mg/dL and the other 2 values are near 100 mg/dL, the investigator may stop or temporarily reduce the dose if, in their judgment, further titration would be hazardous. Doses will be adjusted by 2 to 4 units weekly, or at the investigators discretion to achieve targets. At Week 14, participants will again be required to undergo 14 days of blinded continuous CGM monitoring and a MMTT (only to derive PPG measures) at week 16. The maximum study duration per participant will be 22 weeks. Three site visits, 3 site or home visits, and up to 13 phone contacts are scheduled.

Should a participant not meet the CGM compliance criteria, reinsertion of the CGM device will be allowed.

A detailed description of the assessments performed during each study period and at each visit is provided in below figure ([Figure 1](#))

Figure 1 - Graphical study design

Approximately 100 participants will be enrolled throughout 20 sites in the US.

Oral Antidiabetic Drugs (OAD) and Glucagon-Like-Peptide 1 Receptor Agonists (GLP-1RA)

All participants will be allowed to continue their background OADs (except DPP-4i and SU down-titration) at stable doses and administration timeframes throughout the study period, unless they must be stopped or modified for safety reasons. Any GLP-1RA use (oral or injectable) must also be discontinued prior to Soliqua 100/33 administration.

The analyses of the study will be conducted after completion.

1.2 OBJECTIVES AND ENDPOINTS

Table 2 - Objectives and endpoints

Objectives	Endpoints

Primary
 
 To demonstrate that in participants with T2DM failing to achieve glycemic control (HbA1c \geq9%-13%) on their current regimen of 2+ OADs with or without GLP-1RAs, introduction of Soliqua 100/33 exhibits superiority in terms of time spent in range (70-180 mg/dL) at week 16 compared with baseline, as measured by CGM 	
 Change in the percentage of TIR (70-180 mg/dL) from baseline to week 16

	Objectives	Endpoints
Secondary	
Key Secondary Objective
 
 
• To evaluate the impact of Soliqua 100/33 on measures of glycemic control and variability in participants with T2DM 
Secondary Objective
 
 
• To evaluate the impact of Soliqua 100/33 on other measures of glycemic control and variability in participants with T2DM 	
Key Secondary Endpoints
 
 
• Change (%) from baseline to week 16 in coefficient of variation (CV) 
• Change (mg/dL) from baseline to week 16 in mean daily blood glucose 
• Change (mg/dL) from baseline to week 16 in the maximum PPG exposure in the 4 hours after the breakfast meal (using MMTT data) 
• Change (%) from baseline to week 16 in TAR (>180 mg/dL) 
Secondary Endpoints
 
 
• Proportion (%) of participants achieving CV <36% 
• Change (%) from baseline to week 16 in TIR (70-180 mg/dL) for specific time blocks (6 am-12 pm, 12 pm-6 pm, 6 pm-12 am, 12 am-6 am, and 6 am – 12 am) 
• Proportion (%) of participants achieving Glucose Management Indicator (GMI) <7% and <9% at week 16 
• Change from baseline to week 16 in the 4 hour PPG AUC_{0-4h} after start of the breakfast meal, including associated T_{max} (using MMTT data) 
• Proportion (%) of participants at week 16 who spend <15 minutes/day at a glucose level <54 mg/dL

	Objectives	Endpoints
Tertiary/exploratory	
 To evaluate the impact of Soliqua 100/33 on additional measures of glycemic control and variability in participants with T2DM 	
 Change (mg/dL) from baseline to week 16 in mean of daily difference (MODD) Change (%) from baseline to week 16 in TAR (>250 mg/dL) Change (%) from baseline to week 16 in time below range (TBR); <70 mg/dL) Correlation of change in the percentage of TIR (70-180 mg/dL) and change in patient reported outcome (PRO) from baseline to week 16 Correlation of percentage of TIR (70-180 mg/dL) and HbA1c percentage achieved at week 16 Association of participants reaching 60 units/day insulin glargine U100 and TIR >70% Change in HbA1c percentage from baseline to week 16 Change in the percentage from baseline to week 16 for Time in Tight Range (TITR)(70-140 mg/dL) Proportion of participants with TIR (70–180 mg/dL) > 70% of each day at week 16 Proportion of participants with ≥5% absolute improvement from baseline to week 16 in TIR (70–180 mg/dL) Proportion of participants with ≥10% absolute improvement from baseline to week 16 in TIR (70–180 mg/dL) Proportion of participants with improvement in HbA1c >0.5% points from baseline to week 16 without an increase in TBR (<54 mg/dL) of >0.5% Proportion of participants with ≥10% absolute improvement from baseline to week 16 in TIR (70–180 mg/dL) without an increase in TBR (<54 mg/dL) of >0.5% Proportion of participants with TIR (70–180 mg/dL) > 70% per day and TBR (<70 mg/dL) < 4% per day at week 16

Objectives	Endpoints

PRO Objective
 
 To assess participant-perceived treatment impact on health-related quality of life (HRQoL) and treatment satisfaction 
Safety Objective
 
 To assess the safety and tolerability of Soliqua 100/33 	
PRO Endpoint
 
 Change from baseline to week 16 in diabetes medication treatment satisfaction scores (total score and by subscales), using the DM-SAT questionnaire 
Safety Endpoints
 
Safety evaluations will include evaluation of the following (for 16 weeks):
 
 Overall hypoglycemia Confirmed hypoglycemia 
 ADA Level 1: Measurable glucose concentration <70 mg/dL (3.9 mmol/L) but ≥54 mg/dL (3.0 mmol/L) ADA Level 2: Measurable glucose concentration <54 mg/dL (3.0 mmol/L) that needs immediate action ADA Level 3: Severe event characterized by altered mental and/or physical functioning that requires assistance* from another person for recovery Adverse events (AEs), serious adverse events (SAEs), and adverse events of special interest (AESIs)

1.2.1 Estimands

The primary estimand defined for main endpoints are summarized in [Table 3](#). More details are provided in [Section 4](#).

Table 3 - Summary of primary estimand for main endpoints

Endpoint Category (estimand)	Estimands			
	Endpoint	Analysis Set	Intercurrent event(s) handling strategy	Analysis Set-level summary (Analysis and missing data handling)
Primary objective: To demonstrate that in participants with T2DM failing to achieve glycemic control (HbA1c \geq9%-13%) on their current regimen of 2+ OADs with or without GLP-1RAs, introduction of Soliqua 100/33 exhibits superiority in terms of time spent in range (70-180 mg/dL) at week 16 compared with baseline, as measured by CGM.				
Primary endpoint (treatment policy estimand)	Mean change in percentage of TIR at week 16 from baseline	Efficacy analysis set	Treatment policy strategy ^a .	Mean and 95% (CI) of change in percentage of TIR at week 16 from baseline will be calculated for subjects who have CGM compliance at baseline and week 16. A one sample t-test will be applied to test the significance of changes.
Key Secondary objective: To evaluate the impact of Soliqua 100/33 on measures of glycemic control and variability in participants with T2DM				
Key Secondary endpoint (treatment policy estimand)	Mean percent changes of CV at week 16 from baseline	Efficacy analysis set	Treatment policy strategy ^a	Mean and 95% CI will be calculated for subjects who have CGM compliance at baseline and week 16. A one sample t-test will be applied to test the significance of changes.
	Mean mg/dL change of mean daily blood glucose at week 16 from baseline	Efficacy analysis set	Treatment policy strategy ^a	Mean and 95% CI will be calculated for subjects who have CGM compliance at baseline and week 16. A one sample t-test will be applied to test the significance of changes.
	Mean mg/dL change in maximum PPG exposure in the 4-hour period after the breakfast meal at week 16 from baseline	Enrolled analysis set	Treatment policy strategy ^a	Mean and 95% CI will be calculated on an overall efficacy analysis set. A one sample t-test will be applied to test the significance of changes.
	Mean percent change in TAR >180 mg/dL at week 16 from baseline	Efficacy analysis set	Treatment policy strategy ^a	Mean and 95% CI will be calculated for subjects who have CGM compliance at baseline and week 16. A one sample t-test will be applied to test the significance of changes.

^a The following intercurrent events for the primary estimand will be handled by the treatment policy strategy: initiation of rescue medication other than the study IMP and discontinuation of IMP

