Unless otherwise specified, outcome variables based on CGM data will use subjects in the efficacy analysis set with compliant data at baseline.

Percent time in the glucose range is defined as the total number of 15-minute increments where a participant's blood glucose falls within range of ≥ 70 to ≤ 180 mg/dL (≥ 3.9 to ≤ 10 mmol/L) divided by the total number of observed 15-minute increments in that period. Percent time in range will be calculated for baseline (run-in) and for week 16.

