4.3.2 Main analytical approach

Mean change (in percentage) from baseline and its associated 95% CI will be calculated using subjects in the efficacy analysis set with compliant baseline CGM data. A one-sample t-test will be applied to test the significance of changes at week 16 over baseline (run-in). The statistical test will be a 2-sided at a nominal 5% significance level.

Hypothesis Testing of the Primary Endpoint

H0: There is no improvement in TIR at week 16 compared with baseline.

H1: There is an increase in TIR at week 16 compared with baseline.

A two-sided 95% CI will be presented, superiority versus baseline will be demonstrated if the lower bound is above 0.

Missing data will be handled differently in accordance with the reasons for missing data. If the missing data are due to technical issues with the CGM device (ie, CGM data are not evaluable as per the CGM compliance rule [Section 4.3.1](#) during the 2-week run-in period [baseline] as well as the end of the treatment period [ie, from Weeks 14 to 16], the participant will be excluded from the analysis (missing completely at random [MCAR] approach). For all other reasons the Week 16 assessment will be imputed with the baseline observation carried forward (BOCF); therefore, change from baseline will be 0.

The MCAR assumption will be non-conclusively evaluated by testing the association between the baseline covariates and missing data status at Week 16. Specifically, a contingency table will be constructed based on the missing data status at Week 16 and a given categorical baseline covariate. If all the expected cell counts exceed 5, the association will be tested by chi-square test; otherwise, Fisher's exact test will be used.

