4.3.3 Sensitivity analyses

As a sensitivity analysis, the primary analysis will be repeated to include participants with any missing data due to discontinuation or non-compliant data at Week 16 by imputing with BOCF. The mean and its associated 95% CI will be reported.

As a second sensitivity analysis, the primary analysis will be repeated for all participants in the efficacy analysis set. All missing data at Baseline and Week 16 will be excluded and not imputed, and only compliant CGM data will be utilized. Mean and its associated 95% CI will be reported.

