4.4.1.2 Main analytical approach

The key secondary estimand will be estimated based on the efficacy analysis set using measurements obtained during the study, regardless of intercurrent events. All four endpoints are continuous and will be summarized using the number of observations available, mean, SD, minimum, median, and maximum. Mean changes for continuous outcomes will be presented at baseline and at the end of the treatment period (Week 16). Mean (SD) and associated 95% CI, as well as minimum, median, and maximum values will be provided, and the analysis will be tested with 2-sided tests at 5% significance level.

Key Secondary endpoints will undergo hierarchical testing in the order displayed in [Section 4.6](#), using two-sample t-test. The results of the test will be displayed in a summary table.

Missing data handling of key CGM secondary endpoints will follow the same approach as the primary estimand.

Regarding participants who discontinue treatment early, but complete the early termination visit per protocol and have MMTT collected at the EOT visit, their data will be used if collected on study day 56 or later; otherwise, the week 16 outcome will be imputed. If the week 16 MMTT data were collected prior to day 56 or missed, then the week 16 outcome will be imputed using baseline observation carried forward (BOCF).

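### SAP Table 3 limits the primary and three CGM key secondary analyses to participants compliant at both times, whereas SAP 4.3.2 and the protocol apply BOCF to non-technical missing Week 16 data, and 4.3.2 does not define technical missingness clearly enough to apply its own rule

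*SAP*

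**What the plan says.** **SAP 1.2.1, Table 3.** The last column is meant to give both the analysis and the missing-data handling. For the primary endpoint, CV, mean daily glucose and TAR >180 it says the mean and CI "will be calculated for subjects who have CGM compliance at baseline and week 16". It mentions no imputation. The maximum PPG row has no such limit. The table is introduced as a summary: "More details are provided in" Section 4.

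**SAP 4.3.1.** By default, "outcome variables based on CGM data will use subjects in the efficacy analysis set with compliant data at baseline". This matches the efficacy analysis set in SAP Table 4, which depends on baseline compliance only.

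**SAP 4.3.2.** Participants are excluded when data are missing because of "technical issues with the CGM device (ie, CGM data are not evaluable as per the CGM compliance rule" in 4.3.1, over the run-in as well as the end of treatment. Then: "For all other reasons the Week 16 assessment will be imputed with the baseline observation carried forward (BOCF", so that the change is 0.

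**SAP 4.4.1.2.** "Missing data handling of key CGM secondary endpoints will follow the same approach as the primary estimand".

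**SAP 4.3.3.** In the first sensitivity analysis "the primary analysis will be repeated to include participants with any missing data due to discontinuation or non-compliant data at Week 16", using BOCF. In the second, "All missing data at Baseline and Week 16 will be excluded and not imputed, and only compliant CGM data will be utilized".

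**Protocol.** Table 8-2 and Sections 8.7.2.1, 8.7.3.1 and 8.7.3.3 all apply BOCF to Week 16 data missing for non-technical reasons. Section 8.7.2.1 assigns loss to follow-up and treatment discontinuation to BOCF outright, and 8.7.3.3 gives them as examples.

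**Declared changes.** SAP 5.2 reports none. SAP Table 9 lists the wider compliance definition and two edits to correlation endpoints, but not removal of BOCF.

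**The concern.** This is the missing-data rule for the primary endpoint and for three of the four key secondary endpoints in the testing hierarchy. Two parts of one SAP give different analysed groups, and a programmer could defend either. Under Table 3 the protocol's BOCF is never used in the primary analysis, and the second sensitivity analysis simply repeats the primary.

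Correcting Table 3 to point to 4.3.2 does not finish the job. That section decides who is excluded and who gets BOCF through an *ie* parenthesis that refers back to the compliance rule rather than to the cause of the missing data.

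**Working it through.** **1. Who is analysed, and how.** Take participants in the efficacy set, all compliant at baseline.

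| Week 16 status | Table 3 | 4.3.2, technical = fails the rule in either period | 4.3.2, technical = fails in both periods | Protocol, by cause |
|---|---|---|---|---|
| Compliant CGM | observed | observed | observed | observed |
| Lost or discontinued, no CGM | left out | excluded | BOCF | BOCF (8.7.2.1) |
| CGM worn but not evaluable | left out | excluded | BOCF | excluded as technical (8.7.3.3) |

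On the either-period reading, a dropout with no Week 16 CGM fails the rule and counts as technical, while anyone who passes has a value. No one is left for BOCF, and the result equals Table 3 and the second sensitivity analysis. On the both-periods reading, no one in the efficacy set can have failed at baseline. No one is excluded, and the primary equals the first sensitivity analysis. Neither reading gives the protocol's split.

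**2. The plan's own figure.** Inputs from SAP Section 2: gain 10, SD 25, two-sided alpha 0.05, power 95%, 15% loss, 100 enrolled. n = (25 × (1.960 + 1.645) / 10)² = 81.2, so 82, as stated. Power at 82 is 0.952 by the normal formula and 0.947 by noncentral t. 82 / 0.85 = 96.5, so 97 against the 100 planned.

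**3. Effect of the rule on the estimate.** Assume all 100 are in the efficacy set, m lack usable Week 16 CGM, k of those m are technical and excluded, and those observed gain d = 10 with SD 25. The split k is an assumption, because the documents give none. Then:

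- n = 100 − k and p = (100 − m) / n
- mean = p × d
- variance = p × (25² + d²) − (p × d)²
- power from noncentral t with these values

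For m = 15 and k = 0: p = 0.85, mean 8.5, variance 0.85 × 725 − 72.25 = 544, SD 23.3.

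| m | k | Mean, BOCF | Power, BOCF | Mean, Table 3 | Power, Table 3 |
|---|---|---|---|---|---|
| 5 | 0 | 9.5 | 0.970 | 10.0 (n = 95) | 0.971 |
| 10 | 0 | 9.0 | 0.962 | 10.0 (n = 90) | 0.964 |
| 15 | 0 | 8.5 | 0.950 | 10.0 (n = 85) | 0.954 |
| 15 | 10 | 9.4 | 0.953 | 10.0 (n = 85) | 0.954 |
| 18 | 0 | 8.2 | 0.943 | 10.0 (n = 82) | 0.947 |
| 18 | 10 | 9.1 | 0.945 | 10.0 (n = 82) | 0.947 |

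The rows with m = 18 use 100 − 82, the gap in the plan. Simulation with 15 missing and none technical gave power of 0.954 under both rules. The 95% CI half-width in that case is 4.6 under BOCF and 5.4 under Table 3. With the 16-point improvement that SAP Section 2 also mentions, the means are 13.6 and 16.0.

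**The case against.** **Table 3 has some protocol support.** Protocol 8.7.2.1 defines evaluable data over both periods, and the analysis criteria in protocol 13.9 admit endpoint data on that standard. This stands: the both-times rule did not come from nowhere. But 8.7.2.1 goes on to send loss to follow-up and discontinuation to BOCF, so the definition says what counts as missing, not that the missing are dropped.

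**Intent is not certain.** The first sensitivity analysis is worded as bringing in discontinuers, which suggests that the primary leaves them out. The baseline-only sentence in 4.3.1 is a default that yields to anything specified elsewhere. Both count for Table 3. Against them are the BOCF sentence in 4.3.2, its extension in 4.4.1.2, and a second sensitivity analysis that is redundant if Table 3 is the primary.

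**The summary label.** Table 3 defers to Section 4 for detail, but no text says that Section 4 prevails.

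**The *ie* wording is the protocol's too.** The protocol synopsis and 8.7.3.3 use the same construction. That is right, so the weakness did not begin in the SAP. The protocol, however, anchors BOCF by cause in 8.7.2.1 and in the 8.7.3.3 examples, and SAP 4.3.2 carries over neither.

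**Consequences are limited.** The first sensitivity analysis reports a BOCF mean and CI whichever primary is used, so readers would see that estimate. This stands and limits the seriousness. It does not settle which figure is the headline.

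**Conclusion.** The conflict between Table 3 and SAP 4.3.2 is real and undeclared, and it should be fixed before lock. Confidence is high on that and moderate on how the *ie* parenthesis should be read. With 15 missing, the choice moves the reported TIR gain from 10.0 to between 8.5 and 9.4 points, with power about 95% throughout. This assumes 100 in the efficacy set, a gain of 10 (SD 25) in those observed, and 0 to 10 technical losses.

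A reader might infer more than the documents support:

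- **That Table 3 is plainly a drafting slip.** The evidence on intent is mixed. The protocol's explicit assignment by cause is the better ground for preferring BOCF.
- **That 4.3.2 certainly empties the BOCF group.** It does so on one reading; on the other it empties the exclusion group. The wording fails either way.
- **That Table 3 overstates the effect.** The gaps are the arithmetic of assigning zero change. The documents do not show how participants with missing data fare, so the direction of any bias is unknown.
- **That non-compliant data without a documented device cause belong under BOCF in the primary.** That would be a new rule. Protocol 8.7.3.3 treats non-evaluable CGM as technical, and the first sensitivity analysis already covers these participants.

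**What to change.** 1. In Table 3, change the four CGM rows to the efficacy analysis set, with missing Week 16 data handled as in 4.3.2.
2. In 4.3.2, replace the *ie* parenthesis with the protocol's rule by cause. Week 16 CGM missing because of loss to follow-up, withdrawal or treatment discontinuation gets BOCF. CGM that was worn but is not evaluable under the compliance rule is excluded as technical.
3. In 4.3.3, word the first sensitivity analysis as BOCF for all missing Week 16 data whatever the reason, matching protocol 8.7.2.2. Keep the compliant-only analysis as the second.
4. Tabulate the reasons for missing Week 16 data, which protocol 8.7.3.3 already promises.

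The cost is SAP wording before database lock plus one table that is already promised. No change to the sample size is needed. The downside for the sponsor is that the reported mean may be slightly less favourable than under Table 3.

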2 SAMPLE SIZE DETERMINATION

In LPS16990, a total of 100 participants will be enrolled in the study. Sufficient participants will be screened from 20 sites to include 100 participants, such that approximately 82 evaluable participants complete the study (anticipating that approximately 15% of participants discontinue the study before Week 16).

The sample size is based on the primary objective to demonstrate the significant mean change (increase) in the percentage of TIR (70-180 mg/dL) from baseline to week 16 with sufficient power. A total sample size of 82 evaluable participants has 95% power to detect an absolute increase in TIR means of 10%, assuming a standard deviation (SD) of 25 for the change in TIR, with a two-sided type I error of 0.05. Anticipating a 15% loss to follow-up rate, 100 participants would need to be enrolled.

Assumptions for Sample Size Determinations

- Participants with an HbA1c $\geq 9\%$ are in range 40% of the time or less (Batellino et al 2019).
- Per Vigersky and McMahon, every 10% increase in TIR corresponds to 0.8% HbA1c reduction (Vigersky and McMahon 2019).
- Post hoc analyses from the LixiLan-O study in participants with an HbA1c of $\geq 9\%$ produced an HbA1c reduction of 2.9% at 30 weeks (Davies et al 2019). Therefore, 0.8% HbA1c reduction (considered equal to 16% improvement in TIR) at week 16 seems reasonable.
- Assumption for SD is 25. In the AWARD-4 study in participants with T2DM, the increase in TIR at Week 26 was 20% to 30%, and the SE was approximately 3.0 (corresponding to an SD of approximately 20)

